12. QUALITY CONTROL AND QUALITY ASSURANCE

Pfizer or its agent will conduct periodic monitoring visits during study conduct for studies conducted at non-Pfizer investigator sites, to ensure that the protocol and Good Clinical Practices (GCPs) and/or Good Pharmacoepidemiology Practices (GPP), as relevant, are being followed. The monitors may review source documents to confirm that the data recorded on CRFs [data collection tools (DCTs)] are accurate. The investigator and institution will allow Pfizer monitors/auditors or its agents and appropriate regulatory authorities direct access to

source documents to perform this verification. This verification may also occur after study completion.

During study conduct and/or after study completion, the investigator site may be participant to review by the IRB/EC, and/or to quality assurance audits performed by Pfizer, or companies working with or on behalf of Pfizer, and/or to inspection by appropriate regulatory authorities.

The investigator(s) will notify Pfizer or its agents immediately of any regulatory inspection notification in relation to the study. Furthermore, the investigator will cooperate with Pfizer or its agents to prepare the investigator site for the inspection and will allow Pfizer or its agent, whenever feasible, to be present during the inspection. The investigator site and investigator will promptly resolve any discrepancies that are identified between the study data and the participant's medical records. The investigator will promptly provide copies of the inspection findings to Pfizer or its agent. Before response submission to the regulatory authorities, the investigator will provide Pfizer or its agents with an opportunity to review and comment on responses to any such findings.

For studies conducted at non-Pfizer investigator sites, it is important that the investigator(s) and their relevant personnel are available during the monitoring visits and possible audits or inspections and that sufficient time is devoted to the process.

13. LIMITATIONS OF THE RESEARCH METHODS

The study design is limited by pragmatic considerations around available participants, minimizing burden on young participants and the CCI nature of many of the growth biomarkers.

14. PROTECTION OF HUMAN PARTICIPANTS

14.1. Participant Information and Consent

All parties will comply with all applicable laws, including laws regarding the implementation of organizational and technical measures to ensure protection of participant personal data. Such measures will include omitting participant names or other directly identifiable data on any sponsor forms, reports, publications, or in any other disclosures, except where required by applicable laws.

The personal data will be stored at the study site in encrypted electronic and/or paper form and will be password protected or secured in a locked room to ensure that only authorized study staff have access. The study site will implement appropriate technical and organizational measures to ensure that the personal data can be recovered in the event of disaster. In the event of a potential personal data breach, the study site shall be responsible for determining whether a personal data breach has in fact occurred and, if so, providing breach notifications as required by law.

To protect the rights and freedoms of natural persons with regard to the processing of personal data, when study data are compiled for transfer to Pfizer and other authorized parties, participant names will be removed and will be replaced by a single, specific numerical code, based on a numbering system defined by Pfizer. All other identifiable data transferred to Pfizer or other authorized parties will be identified by this single, participant-specific code. The investigator site will maintain a confidential list of participants who participated in the study, linking each participant's numerical code to his or her actual identity. In case of data transfer, Pfizer will maintain high standards of confidentiality and protection of participant's personal data consistent with the clinical study agreement (CSA) and applicable privacy laws.

The informed consent[/assent] documents and any participant recruitment materials must be in compliance with ICH GCP, local regulatory requirements, and legal requirements, including applicable privacy laws.

The informed consent[/assent] documents used during the informed consent process and any participant recruitment materials must be reviewed and approved by Pfizer, approved by the IRB/EC before use, and available for inspection.

The investigator must ensure that each study participant[, or his or her legally acceptable representative, or parent(s) or legal guardian if a minor,] is fully informed about the nature and objectives of the study, the sharing of data relating to the study and possible risks associated with participation, including the risks associated with the processing of the participant's personal data. The investigator further must ensure that each study participant [, or his or her legally acceptable representative, or parent(s) or legal guardian if a minor,] is fully informed about his or her right to access and correct his or her personal data and to withdraw consent for the processing of his or her personal data.

Whenever consent is obtained from a participant's [legally acceptable representative/parent(s) or legal guardian], the participant's assent (affirmative agreement) must subsequently be obtained when the participant has the capacity to provide assent, as determined by the IRB/EC. If the investigator determines that a participant's decisional capacity is so limited that he or she cannot reasonably be consulted, then, as permitted by the IRB/EC and consistent with local regulatory and legal requirements, the participant's assent may be waived with source documentation of the reason assent was not obtained. If the study participant does not provide his or her own consent, the source documents must record why the participant did not provide consent (eg, minor, decisionally impaired adult), how the investigator determined that the person signing the consent was the participant's legally acceptable representative, the consent signer's relationship to the study participant (eg, parent, spouse), and that the participant's assent was obtained or waived. If assent is obtained verbally, it must be documented in the source documents.

If the study includes minor participants who reach the age of majority during the study, as recognized under local law, they must re consent as adults to remain in the study. If the enrollment of emancipated minors is permitted by the study age criteria, the IRB/EC, and local law, they must provide documentation of legal status to give consent without the permission of a parent or legal guardian.

The investigator, or a person designated by the investigator, will obtain written informed consent from each participant [or the participant's legally acceptable representative, parent(s), or legal guardian and the participant's assent, when applicable,] before any study-specific activity is performed, unless a waiver of informed consent has been granted by an IRB/EC. The investigator will retain the original of each participant's signed consent/assent document.

14.1.1. Screen Failures

A participant who fail inclusion and/or exclusion criteria may be rescreened for the study. The re-screening can occur at a time interval considered appropriate by the investigator. If a participant is eligible to enter the study after having previously failed screening, they will be assigned a new identification number. However, participants who are withdrawn from the study will not be replaced.

A minimal set of screen failure information is required to ensure transparent reporting of screen failure participants, to meet the Consolidated Standards of Reporting Trials (CONSORT) publishing requirements and to respond to queries from regulatory authorities. Minimal information includes demography, screen failure details, and eligibility criteria.

14.2. Participant Withdrawal

Participants may withdraw from the study at any time at their own request, or they may be withdrawn at any time at the discretion of the investigator or sponsor for safety, behavioural, or administrative reasons. In any circumstance, every effort should be made to document participant outcome, if applicable. The investigator should inquire about the reason for withdrawal and follow-up with the participant regarding any unresolved adverse events.

If the participant withdraws from the study, and also withdraws consent for disclosure of future information, no further evaluations should be performed, and no additional data should be collected. The sponsor may retain and continue to use any data collected before such withdrawal of consent.

14.2.1. Lost to Follow-up

The study site personnel must attempt to contact the participant's parent(s)/legal guardian(s) and counsel the parent(s)/legal guardian(s) on the assigned visit schedule and ascertain whether or not the participant and the parent(s)/legal guardian(s) wish study participation to continue.

A participating participant will be considered lost to follow-up in case a 1-year period has passed without return for scheduled visits and if the parent(s)/legal guardian(s) are unable to be contacted by the study site personnel on 3 occasions.

Before a participant is deemed lost to follow-up, the investigator or designee must make every effort to regain contact with the parent(s)/legal guardian(s) in the form of (where possible) 3 telephone calls and, if necessary, a certified letter to the parent(s)/legal guardian(s) last known mailing address or local equivalent methods. These contact attempts should be documented in the participant's medical record.

Should the parent(s)/legal guardian(s) continue to be unreachable, the participant will be considered as withdrawn from the study with the reason category "lost to follow-up."

14.3. Institutional Review Board (IRB)/Independent Ethics Committee (IEC)

It is the responsibility of the investigator to have prospective approval of the study protocol, protocol amendments, informed consent/assent documents, and other relevant documents, eg, recruitment advertisements, if applicable, from the IRB/IEC. All correspondence with the IRB/IEC should be retained in the investigator file. Copies of IRB/IEC approvals should be forwarded to Pfizer.

The only circumstance in which an amendment may be initiated prior to IRB/IEC approval is where the change is necessary to eliminate apparent immediate hazards to the participants. In that event, the investigator must notify the IRB/IEC and Pfizer in writing immediately after the implementation.

14.4. Ethical Conduct of the Study

The study will be conducted in accordance with the protocol, legal and regulatory requirements, and the general principles set forth in the International Ethical Guidelines for Biomedical Research Involving Human Participants (Council for International Organizations of Medical Sciences 2002), ICH Guideline for Good Clinical Practice, and the Declaration of Helsinki.

15. MANAGEMENT AND REPORTING OF ADVERSE EVENTS/ADVERSE REACTIONS

REQUIREMENTS

This study includes qualifying diagnostic or monitoring procedures required per protocol to collect clinical data needed to meet the study objectives, which are not standard-of-care but that do not pose more than a minimal risk or burden to the study participant. The qualifying procedures in this study are:

Qualifying diagnostic or monitoring procedure(s)	Recording Time Period
Biomarker Blood Sample (Venous)	12 hours

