5. SCHEDULE OF ACTIVITIES

STUDY PROCEDURES and **ASSESSMENTS** sections of the protocol for detailed information on each procedure and assessment required for compliance with the protocol.

The investigator may schedule visits (unplanned visits) in addition to those listed in the schedule of activities table, in order to conduct evaluations or assessments required to protect the well-being of the participant.

Procedure/Assessment	Screening Visit ^a	Baseline Visit ^b	Every 3 Months ^c (±3 weeks)	End of Study Visit ^d (±3 weeks)
Informed Consent & Assent (as applicable)	X			
Eligibility criteria	X	X		
Demographics	X			
Specific Medical & Surgical History	X	X		
Physical Examination		X	X	X
Genetic Confirmation of Achondroplasia ^e		X		
Anthropometric Measurements		X	X	X
Achondroplasia-related complications, tests & treatments		X	X	X
Non-achondroplasia-related important medical conditions and treatments ^f		X ^f	X ^f	X
Tanner Stage of Puberty ^g		X ^g	X ^g	X
Collection of Biomarker Blood Sample ^h		X	(X) Every 12 Months	
Concomitant treatments	X		X	→
Adverse event monitoring	X	X	→	→
QoLISSY Brief tool (HRQoL)		X	X	X
Childhood Health Assessment Questionnaire (CHAQ)		X	X	X
Physical activity via accelerometry (digital wearable sensors) ⁱ (selected sites only)	X	X	X	X
Gait walking assessment ^j (selected sites only)	X	X	X	X
Wearability Questionnaire of digital sensors ^k (selected sites only)	X	X	X	X

Abbreviations: → = ongoing/continuous event.

- a. Screening may be scheduled within 1 month prior to the Baseline visit.
- b. Screening visit and Baseline visit can be combined, if applicable.
- c. Three-month follow-up visits are scheduled relative to the date the Baseline Visit was conducted.
- d. The End of study visit is conducted if any one of the termination criteria listed are met or after a decision is made by the investigator to withdraw the participant from the study. The end of study visit may be combined with a three-monthly visit.
- e. If not available in medical records, then the result of genetic testing should become available as soon as possible, but not later than prior to end of study visit.
- f. Any important non-achondroplasia related important medical condition (s) that may potentially jeopardize the participant's health and any treatment based on the medical judgment of the investigator that may affect the participant's growth trajectory (see [Section 11.3](#)).

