- g. Tanner Stage of Puberty: Only for participants ≥ 7 years of age (providing the investigator confirms there is no suspicion of a diagnosis of precocious puberty).
- h. Fasting 8-hour blood sample for biomarker analyses should be drawn in the morning. A less than 8-hour prior to biomarker analysis should be recorded in the source notes.
- i. Physical activity: This assessment is optional for participants and will be performed at selected sites. Wrist and lumbar digital wearable sensors will be provided to the participant and worn continuously for 14 days after each three-month visit. The sensors will be returned by the participant to the site via a self-addressed stamped envelope after the 14-day period of data collection. Only for participants ≥ 2 years who can walk independently. Participants with any skin nickel allergy or silicone or adhesive allergy as well as participants with any implanted medical device (ie, pacemaker or electric pumps) should excluded from participation in the physical activity assessments.
- j. Walking Assessment: This assessment is optional for participants and will be performed at selected sites. The walking assessment will be performed once per participant during any given in-clinic visit. Only for participants ≥ 2 years who can walk independently. Participants with any skin nickel allergy or silicone or adhesive allergy as well as participants with any implanted medical device (ie, pacemaker or electric pumps) should excluded from participation in the physical activity assessments.
- k. Wearability Questionnaire: This assessment is only required for participants who are performing the optional physical activity activity. The participant/caregiver will rate the overall comfort of the wrist and lumbar devices at the conclusion of the 14 days of wearing the sensors. This will be returned to the site via self-addressed stamped envelope along with the sensors.

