The potential risks of study participation include risks of medical evaluation, anthropometric measurements and venepuncture. The risks associated with participation in this study are considered minimal, since the nature of the anthropometric assessments and medical observations tracked and documented are all considered to be established as part of current standard of care (SOC). The extent of repeated anthropometric measurements as well as repeated venepuncture may not be considered SOC at all sites; however, the frequency is considered acceptable to be associated with a minimal risk. There is no direct benefit to the participant, their parent(s) or the health care providers other than being able to track the participating participant's development compared to their peers, something that will be

increasingly important with disease-modifying therapies being developed targeting the consequences of the mutation of the FGFR3 on the human body.

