8.1.3. Variables

Variable	Role	Data source(s)	Operational definition
Anthropometric Measurements	Analysis of growth parameters	Anthropometric measurements	Collection every 3 months & End of Study
Tanner Staging	Assess stage of sexual development	Physical Examination	Collection every 3 months & End of Study
Achondroplasia related complications, tests & treatments	Characterize treatments for Achondroplasia	Medical Records	Collection every 3 months & End of Study
Non-Achondroplasia	Characterize medical	Medical records	Collection every 3 months

Variable	Role	Data source(s)	Operational definition
co-morbidities and treatments	history		& End of Study
Biomarker Blood Sample	Analysis for potential biomarkers of bone growth	Blood sample	Blood sample every 12 months & End of Study
Activity Tracker & Gait Measurement	Analysis of daily activity & gait when walking	Activity Tracker & Gait Mat	Collection every 3 months & End of Study
Quality of Life	Assess Quality of Life in Participant & families with Achondroplasia	Questionnaire	Collection every 3 months & End of Study

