15.1. Adverse Events (AE)

An AE is defined as any untoward medical occurrence and can therefore be any unfavorable and unintended sign (including an abnormal laboratory finding), symptom, or disease, whether or not related to the participant's participation in the study.

Any AE that occurs from the time the participant consents to the clinical research through and including 12 hours after completion of the qualifying procedure must be recorded.

The investigator is required to assess whether the AE may be related to the participant's participation in the study. All AEs (ie, serious and non-serious, including those attributed to qualifying procedure identified as research-related injury) are collected in the clinical study database.

The investigator must pursue and obtain information adequate to determine the outcome of the AE and to assess whether it meets the criteria for classification as a research-related injury requiring immediate notification to Pfizer as described below.

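### The stated adverse-event recording periods do not clearly cover the 14 days of sensor wear scheduled after the End of Study visit

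*Protocol*

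**What the plan says.** **Sensor wear.** The document history (Protocol Section 4) lists optional activity tracking among the additions in version 3.0. Section 5, footnote i, has the sensors "worn continuously for 14 days after each three-month visit" and then posted back. The Section 5 row "Physical activity via accelerometry (digital wearable sensors") is marked at Screening, Baseline, every 3 months and End of Study. In the Section 8.1.3 table, the row "Activity Tracker & Gait Measurement" is likewise to be collected every 3 months and at End of Study.

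**Recognised risk.** Footnotes i and j to Section 5 keep out "Participants with any skin nickel allergy or silicone or adhesive allergy". The Section 6 risk statement does not name the sensors: "The potential risks of study participation include risks of medical evaluation, anthropometric measurements and venepuncture".

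**AE recording.** The Section 15 table has one entry, "Biomarker Blood Sample (Venous"), with 12 hours beside it. Section 15.1 starts recording at consent and continues "through and including 12 hours after completion of the qualifying procedure must be recorded". Other text is broader. Section 5 shows AE monitoring as continuous after Baseline. The Section 15.2 table puts every non-serious AE on the case report form. The reporting-period text in Section 15.2 runs from consent to the end of an observation period that is not defined.

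**After the wear.** Footnote k and Section 9.16 describe a questionnaire, returned with the sensors, on which the comfort of the devices is rated.

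**The concern.** Sensor wear is done only for the study, in children from about 2 years of age, and the protocol itself anticipates skin reactions to the materials. Yet the end of AE recording in Section 15.1 is set by a different procedure, the blood draw. Where wear outlasts the recording period, a rash could go unrecorded, or be recorded at one site and not at another. The protocol's minimal-risk position could then not be checked against data for this procedure.

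The exposed period is the wear after End of Study. No later visit is scheduled at which a reaction could be reported.

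**Working it through.** The plan gives no figure to reproduce. The check sets the wear period against each stated recording period.

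**Inputs**
- Length of wear: 14 days (Section 5, footnote i), so 14 × 24 = 336 hours.
- Recording period attached to the blood draw: 12 hours (Section 15 table).
- Blood draw: the Section 5 row "Collection of Biomarker Blood Sample" is marked at Baseline and every 12 months, with no mark at End of Study. Section 8.1.3 adds a draw at End of Study.
- End of the study: the last visit of the last child (Section 8.1).

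**Step 1. Wear between visits.** Under the continuous monitoring in Section 5 and the Section 15.2 table and reporting period, an AE during any wear completed before End of Study is recordable, whether or not sensors are on the qualifying list. Only the Section 15.1 wording stands in the way. Suppose, for illustration, a child leaves at month 57 with the last annual draw at month 48 and no draw at exit. Section 15.1 alone would leave out all but 12 hours of the wear after month 48, and all of the wear after months 51, 54 and 57: 13.5 + 3 × 14 = 55.5 days. Section 15.2 would cover all of this except the wear after month 57. For wear between visits the defect is therefore the conflict between Sections 15.1 and 15.2.

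**Step 2. Wear after End of Study.**

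| Reading | Hours covered, of 336 |
|---|---|
| Section 15.1, blood drawn at End of Study | at most 12 (12/336 = 3.6%) |
| Section 15.1, no blood drawn at that visit | 0 |
| Section 15.2, observation ends at the child's last visit | 0 |
| Section 15.2, observation ends with the whole study (Section 8.1) | up to 336 for earlier leavers, 0 for the last child |

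The 12 hours in the first row assume that wear starts as the draw ends. The other 336 − 12 = 324 hours (13.5 days) are outside.

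**Step 3. Finding the event.** Section 5 shows no visit or contact after End of Study. The sensors come back by post with a form described only as a comfort rating. Even on a generous reading of the observation period, no stated step asks about a reaction during the last wear.

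**The case against.** The strongest reply is that AE recording is not limited to events caused by a listed procedure. Section 15.1 itself counts any untoward occurrence, related or not, and Sections 5 and 15.2 record all AEs over the study. That stands for wear between visits, and it shows that absence from the Section 15 list does not itself exclude sensor events.

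The table is also described as listing procedures that the protocol requires, and sensors are optional. This may explain the omission. It does not cover a child who accepts the sensors.

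Wear after End of Study is partly inferred. Footnote i speaks of three-monthly visits, and some marks in these rows cannot be literal: the wearability questionnaire is marked at Screening, before any wear. But Section 8.1.3 separately names End of Study, and footnote d lets that visit coincide with a three-monthly one. If no such wear is meant, the two tables need correcting.

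The undefined observation period could be stretched to include the last wear, and medically important research-related injury (Section 15.2) has no stated time limit. So serious harm caused by participation must be notified in any case. What remains is mainly non-serious skin events.

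A reader might infer a much larger gap: 13.5 of every 14 wear days (96%), or 21 wears × 14 = 294 days per child. The documents do not support either. Section 15.1 runs from consent; it does not open a 12-hour window for each wear. For a child with 21 wears and a draw at month 60, even Section 15.1 leaves out only 13.5 of 294 days (4.6%). The 294 days are total possible wear, not uncovered wear.

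**Conclusion.** The concern holds for the wear after End of Study. Under Section 15.1 at most 12 of its 336 hours are covered, and none if no blood is drawn then. Under Section 15.2 none is covered if observation ends at the child's last visit. If it ends with the whole study, only the last child's final wear is outside. Reconciling Sections 15.1 and 15.2 settles the wear between visits, but settles the final wear only if the agreed end point reaches sensor return.

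The size is one 14-day period per child who does End of Study wear, in an optional assessment at selected sites. This assumes that the End of Study entries in Sections 5 and 8.1.3 mean a new wear. Anthropometric endpoints are not affected.

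It would go too far to say that families are not told of the skin risk or that the form cannot capture a reaction. The consent pages and the questionnaire itself are not available here, and the Section 6 list of risks is not worded as exhaustive. The change is still worth making, because a stated rule would otherwise end AE capture during a study procedure in children, and the repair is cheap.

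**What to change.** 1. Add sensor wear to the Section 15 table with a recording period that runs through sensor return. Alternatively, state that AE recording for sensor participants continues until the last sensors are returned.
2. Reconcile the Section 15.1 end point with the Section 15.2 reporting period, and define the end of the observation period.
3. Add one skin-reaction item to the wearability questionnaire, which is already posted back with the sensors.
4. If no wear is intended after End of Study, correct the accelerometry entries in Sections 5 and 8.1.3 in place of extending recording past that visit.

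Naming the sensors in the Section 6 risk statement would be tidy but is optional.

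The cost is a protocol wording change, one questionnaire item and slightly more AE entry at the selected sites. No visit is added and no endpoint changes.
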